6.2.2. Analysis of Solicited AE

Frequencies and % of subjects experiencing each adverse event will be presented for each symptom severity. Summary tables showing the occurrence of any local or systemic reaction overall and at each time point will also be presented (see Appendix 1 Table 4.1.3 and 4.2.3).

Post-vaccination adverse events reported from Day 1 to Day 7 will be summarized by maximal severity. The severity of local adverse events for subjects < 6 years of age will be categorized as follows. Injection-site erythema and induration: absent (0 to 9 mm), mild (10 to 25 mm), moderate (26 to 50 mm), severe (> 50 mm); injection-site tenderness: none, mild (minor light reaction to touch), moderate (cried or protested to touch), severe (cried when injected limb was moved). For subjects \geq 6 years, injection-site erythema and induration absent (1 to 24 mm), mild (25 to 50 mm), moderate (51 to 100 mm), severe (>100 mm); pain: none, mild (present but does not interfere with activity), moderate (interferes with activity), severe (prevents daily activity).

For subjects \geq 6 years of age, the severity of systemic adverse events (i.e., chills, nausea, malaise, generalized myalgia, generalized arthralgia, headache) occurring up to 7 days after each vaccination will be categorized as none, mild (present but not interfering with daily activity), moderate (some interference with daily activity), and severe (prevents daily activity) except for rash, which will be

	CONFIDENTIAL :	Last Update Date
	THIS DOCUMENT AND INFORMATION CONTAINED HEREIN IS PROPRIETARY TO COMPANY AND IS NOT TO BE DISCLOSED WITHOUT THE WRITTEN PERMISSION OF COMPANY.	20-APR-2018
STATISTICAL ANALYSIS PLAN(V6.0)		

categorized as none, urticarial, or other.

For subjects < 6 years of age, the severity of systemic adverse events occurring up to 7 days after each vaccination will be categorized as follows. Change in eating habits : none (no change in appetite), mild (eating less than normal for 1 to feeds), moderate (missed 1 or 2 feeds), severe (missed more than 2 feeds); sleepiness : none (no change in alertness), mild (shows an increased alertness), moderate (sleeps through feeds), severe (sleeps most of the time and it is hard to arouse him/her); irritability : none (no change in child disposition), mild (requires more cudding and he/she is less playful than usual), moderate (more difficult to settle), severe (unable to console); rash : none, urticarial, or other; vomiting : none, mild (1-2 episodes/24 hours), moderate (>2 episodes/24 hours), severe (requires outpatient hydration); diarrhea : none (fewer than 2 loose stools/24 hours), mild (2-3 loose stools or < 400 gms/24 hours), moderate (4-5 stools or 400-800 gms/24 hours), severe (6 or more watery stools or > 800 gms/24 hours or requires outpatient IV hydration).

Body temperature will be categorized as <38°C (no fever), ≥38°C (fever) and will be summarized by 0.5°C increments from 36.0°C up to ≥40°C. Additionally, no fever vs. fever will be reported.

Each local and systemic adverse event will also be categorized as none vs. any.

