4.1 Safety Set

Table 4.1.1 Summary of Injection site Reaction by Max severity

Safety Set		1*	2*	3*	4*	Total
		n (%)				
Injection site	Pain					
Reactions	Erythema					

STATISTICAL ANALYSIS PLAN(V1.0)

	Induration				
--	------------	--	--	--	--

* Mild(1), Moderate(2), Severe(3) : Pain

* 1-25(1), 26-50(2), 51-100(3), >100(4) : Erythema, Induration

Table 4.1.2 Summary of Systemic Reaction by Max severity

Safety Set		1*	2*	3*	Total
		n (%)	n (%)	n (%)	n (%)
Systemic Reactions	Chills				
	Nausea				
	Malaise				
	Myalgia				
	Arthralgia				
	Headache				
	Rash				

* Mild(1), Moderate(2), Severe(3) : Chills, Nausea, Malaise, Myalgia, Arthralgia, Headache

* Urticarial(1) : Rash

Table 4.1.3 Summary of Solicited AE by day

Safety Set		30 min	6hr	2	3	4	5	6	7	Total
		n (%)	n (%)	n (%)	n (%)	n (%)	n (%)	n (%)	n (%)	n (%)
Injection site Reactions	Pain									
	Erythema									
	Induration									
	Sub Total									
Systemic Reactions	Chills									
	Nausea									
	Malaise									
	Myalgia									
	Arthralgia									
	Headache									
	Rash									
Sub Total										
Total										

	CONFIDENTIAL :	Last Update Date
	THIS DOCUMENT AND INFORMATION CONTAINED HEREIN IS PROPRIETARY TO COMPANY AND IS NOT TO BE DISCLOSED WITHOUT THE WRITTEN PERMISSION OF COMPANY.	06-MAR-2013
STATISTICAL ANALYSIS PLAN(V1.0)		

Table 4.1.4 Summary of Fever

Safety Set		Total n (%)
	Fever	
	No fever	
	Total	
Temperature(°C)	36-36.5	
	36.5-37	
	37-37.5	
	37.5-38	
	38-38.5	
	38.5-39	
	39-39.5	
	39.5-40	
	>40	

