4.1 Safety Set

Table 4.1.1 Summary of Local AE Max severity (<6 years)

Safety Set		1*	2*	3*	4*	Total
		n (%)				
Local AE	Injection site tenderness					
	Injection site erythema					
	Injection site induration					

* Mild(1), Moderate(2), Severe(3) : Injection site tenderness

* 0-9(1), 10-25(2), 26-50(3), >50(4) : Injection site erythema, Injection site induration

Table 4.1.2 Summary of Local AE Max severity (≥6 years)

Safety Set		1*	2*	3*	4*	Total
		n (%)				
Local AE	Injection site pain					
	Injection site erythema					
	Injection site induration					

* Mild(1), Moderate(2), Severe(3) : Injection site pain

* 1-24(1), 25-50(2), 51-100(3), >100(4) : Injection site erythema, Injection site induration

Table 4.1.3 Summary of Local AE by Max severity

Safety Set		1*	2*	3*	4*	Total
		n (%)				
Age (2-23 months)	Injection site tenderness					
	Injection site erythema					
	Injection site induration					
Age (2-5)	Injection site tenderness					
	Injection site erythema					
	Injection site induration					
Age (6-10)	Injection site pain					

Safety Set		1*	2*	3*	4*	Total
		n (%)				
	Injection site erythema Injection site induration					
Age (11-18)	Injection site pain Injection site erythema Injection site induration					
Age (19-34)	Injection site pain Injection site erythema Injection site induration					
Age (35-55)	Injection site pain Injection site erythema Injection site induration					
Age (≥56)	Injection site pain Injection site erythema Injection site induration					

* Mild(1), Moderate(2), Severe(3) : Injection site tenderness, Injection site pain

* 0-9(1), 10-25(2), 26-50(3), >50(4) : Injection site erythema, Injection site induration (Age < 6 years)

* 1-24(1), 25-50(2), 51-100(3), >100(4) : Injection site erythema, Injection site induration (Age ≥ 6 years)

Table 4.1.4 Summary of Systemic AE by Max severity (<6 years)

Safety Set		1*	2*	3*	Total
		n (%)	n (%)	n (%)	n (%)
Systemic AE	Change in eating habits Sleepiness Irritability Vomiting Diarrhea Rash Fever				

* Mild(1), Moderate(2), Severe(3) : Change in eating habits, Sleepiness, irritability, vomiting, diarrhea,

* None(1), Urticarial(2), Other(3) : Rash

* ≥38°C(1) : Fever

Table 4.1.5 Summary of Systemic AE by Max severity(≥ 6 years)

Safety Set		1*	2*	3*	Total
		n (%)	n (%)	n (%)	n (%)
Systemic AE	Chills				
	Nausea				
	Malaise				
	Myalgia				
	Arthralgia				
	Headache				
	Rash				
	Fever				

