* Mild(1), Moderate(2), Severe(3) : Chills, Nausea, Malaise, Myalgia, Arthralgia, Headache

*None(1), Urticarial(2), Other(3) : Rash

* $\geq 38^{\circ}\text{C}$ (1) : Fever

Table 4.1.6 Summary of Systemic AE by Max severity

Safety Set		1*	2*	3*	Total
		n (%)	n (%)	n (%)	n (%)
Age (2-23 months)	Change in eating habits				
	Sleepiness				
	Irritability				
	Vomiting				
	Diarrhea				
	Rash				
	Fever				
Age (2-5)	Change in eating habits				
	Sleepiness				
	Irritability				
	Vomiting				
	Diarrhea				
	Rash				
	Fever				
Age (6-10)	Chills				
	Nausea				

Safety Set		1*	2*	3*	Total
		n (%)	n (%)	n (%)	n (%)
	Malaise Myalgia Arthralgia Headache Rash Fever				
Age (11-18)	Chills Nausea Malaise Myalgia Arthralgia Headache Rash Fever				
Age (19-34)	Chills Nausea Malaise Myalgia Arthralgia Headache Rash Fever				
Age (35-55)	Chills Nausea Malaise Myalgia Arthralgia Headache Rash Fever				
Age (≥56)	Chills Nausea Malaise Myalgia				

Safety Set		1*	2*	3*	Total
		n (%)	n (%)	n (%)	n (%)
	Arthralgia				
	Headache				
	Rash				
	Fever				

* Mild(1), Moderate(2), Severe(3) : Chills, Nausea, Malaise, Myalgia, Arthralgia, Headache, Change in eating habits, Sleepiness, irritability, vomiting, diarrhea,

*None(1), Urticarial(2), Other(3) : Rash

* $\geq 38^{\circ}\text{C}$ (1) : Fever

Table 4.1.7 Summary of Solicited AE by day (<6 years)

Safety Set		30 min	6hr	2 days	3 days	4 days	5 days	6 days	7 days	Total
		n (%)	n (%)	n (%)	n (%)	n (%)	n (%)	n (%)	n (%)	n (%)
Solicited AE	Local AE									
	Injection site tenderness									
	Injection site erythema									
	Injection site induration									
	Systemic AE									
	Change in eating habits									
	Sleepiness									
	Irritability									
	Vomiting									
	Diarrhea									
	Rash									
	Fever									
Total										

Table 4.1.8 Summary of Solicited AE by day (≥ 6 years)

Safety Set		30 min n (%)	6hr n (%)	2 days n (%)	3 days n (%)	4 days n (%)	5 days n (%)	6 days n (%)	7 days n (%)	Total n (%)
Solicited AE	Local AE									
	Injection site pain Injection site erythema Injection site induration									
	Systemic AE									
	Chills Nausea Malaise Myalgia Arthralgia Headache Rash Fever									
Total										

Table 4.1.9 Summary of Solicited AE by day

Safety Set		30 min n (%)	6hr n (%)	2 days n (%)	3 days n (%)	4 days n (%)	5 days n (%)	6 days n (%)	7 days n (%)	Total n(%)
Age (2-23 months)	Injection site tenderness									
	Injection site erythema									
	Injection site induration									

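### Maximal severity is undefined for rash type, and the shell codes, if read as an order, would show a subject with both rash types as Other only

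*SAP*

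**What the plan says.** SAP V6.0, section 6.2.2, sets the general rule: "Post-vaccination adverse events reported from Day 1 to Day 7 will be summarized by maximal severity".

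For subjects of 6 years and over, the systemic events are graded mild to severe, and rash is set apart: "severe (prevents daily activity) except for rash, which will be" "categorized as none, urticarial, or other". For subjects under 6 years, rash sits in the list of severity categories with no such exception: "rash : none, urticarial, or other". Protocol section 7.6.2 uses the same three categories. Neither document says how to count a subject who reports both types during the week.

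Section 6.2.2 refers the reader to Appendix 1 for table shells. The latest Appendix 1 supplied belongs to V4.0. There rash is a row in the max-severity tables for systemic events, for example "Table 4.1.4 Summary of Systemic AE by Max severity (<6 years". The footnote is "None(1), Urticarial(2), Other(3) : Rash", repeated for both age ranges and both analysis sets (Tables 4.1.4-4.1.6 and 4.2.4-4.2.6). V2.0 and V3.0 carry the same key. V1.0 had only "Urticarial(1) : Rash", with no code for other rash.

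Section 6.2.2 also provides a dichotomy: "Each local and systemic adverse event will also be categorized as none vs. any".

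**The concern.** A maximum needs an ordered scale. Mild, moderate and severe form one; none, urticarial and other do not. Section 6.2.2 states the maximum rule without exempting rash, and the only ordering on paper ranks an unspecified rash above urticaria. A programmer who follows the shells literally will hide some urticaria. One who does otherwise will be making up a rule that the SAP does not contain.

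Solicited events are part of the primary objective, and urticarial rash is the solicited item closest to an allergic reaction. In the supplied shells, the max-severity tables are the only solicited-event tables that show rash type. The incidence and by-day tables list rash without type, and the none-versus-any summary drops type by design. A subject misplaced here is therefore not recovered as urticarial in any other solicited table.

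**Working it through.** The plan states no figure for this point, so there is none to reproduce. The check applies the rule literally to the codes.

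**Inputs.** One value per subject over Days 1-7, the maximum (SAP V6.0, 6.2.2). Codes None = 1, Urticarial = 2, Other = 3 (SAP V4.0, Appendix 1). Planned evaluable subjects: 3,000 aged 2-55 years and 600 aged 2-23 months (SAP V6.0, 2.2).

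**Three example records.**
- Urticarial on Day 1, other on Day 4: max(2, 3) = 3, shown as Other.
- Urticarial only: 2, shown as Urticarial.
- Other only: 3, shown as Other.

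Recoding None to 0 changes nothing, because the result depends only on 2 against 3.

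**All seven-day patterns.** Three states over seven days give 3^7 = 2,187 patterns.
- At least one urticarial day: 2,187 − 2^7 = 2,059.
- Urticarial days and no other-rash day: 2^7 − 1 = 127. All have maximum 2.
- Both types: 2,059 − 127 = 1,932. All have maximum 3.

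These are counts of patterns, not probabilities. They show that the result has no exceptions: every mixed week goes to Other, and no week without urticaria goes to Urticarial. The Other column would then mean *ever had another rash*, while the Urticarial column would mean *had urticaria and nothing else*. With the order reversed, no urticaria is lost, but Other is masked in mixed weeks instead.

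**Size.** Let p be the share of subjects who ever have urticaria in the week, and q the share of those who also report another rash type on a different day. True count = N·p; shown count = N·p·(1 − q); fraction lost = q. The documents give neither p nor q. With p assumed at 0.1-1% and q at 5-50%:

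| N | p | true count | shown, q = 5% | shown, q = 50% |
|---|---|---|---|---|
| 3,000 | 0.1% | 3 | 2.85 | 1.5 |
| 3,000 | 1% | 30 | 28.5 | 15 |
| 600 | 0.1% | 0.6 | 0.57 | 0.3 |
| 600 | 1% | 6 | 5.7 | 3 |

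Under these assumptions, between 3 − 2.85 = 0.15 and 30 − 15 = 15 subjects move in the older cohort, and between 0.6 − 0.57 = 0.03 and 6 − 3 = 3 in the infants.

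**The case against.** The strongest reply is that the codes are a display key and not a scale. In the V4.0 shells, column 1 means mild for most systemic events, no rash for rash, 38°C or above for fever, and 0-9 mm for erythema under 6 years. No text says that the maximum is taken on these numbers, and for ages 6 and over rash is worded as an exception to grading. This stands: counting a mixed subject as Other is an inference from an unstated rule. It does not supply the missing rule, though. The exception swaps grades for types without taking rash out of the maximum summary, and under 6 years there is no exception.

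Second, the codes come from V4.0, and the V5.0 and V6.0 shells are not among the documents. Also true. However, the V6.0 revision table describes the V5.0 appendix change as adding the disclosure analyses. For V6.0 it lists wording, the criteria for medically attended events and the label analyses. No logged change names rash coding.

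Third, the mechanism needs rash type recorded day by day, and no Diary Card or CRF is available to show that. This cannot be settled from the documents.

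Fourth, urticaria has other routes into the report. Immediate reactions go on the Adverse Events CRF (protocol 6.2.1), and medically attended, serious and continuing solicited events are tabulated by preferred term (SAP V6.0, 6.2.3). These recover some cases but do not give a count of subjects with urticaria on Days 1-7.

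**Conclusion.** The point holds as a conditional one. Maximal severity is not a valid summary of rash type, and the plan has no rule for a subject with both types. If the order in the latest supplied shells is followed, such subjects appear only as Other, and the error in the urticaria count runs one way, downward.

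A reader might infer more: that the plan definitely counts these subjects as Other, that their urticaria vanishes from the report, and that the hypersensitivity signal is biased by a sizeable percentage. The documents do not support this. Use of the codes as a scale is not stated, the subject remains in the any-rash and by-day counts, and only the type breakdown is at risk. Nor can a percentage be defended. Assuming that 20-50% of subjects with rash have urticaria and 5-10% have both types would give a loss of 10% (0.05/0.50) to 50% (0.10/0.20), but both inputs are invented for illustration.

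The conclusion rests on three things: the V4.0 codes still being in use, the maximum being taken in their order, and type being recorded by day. The size is unknown and the absolute numbers are probably small. For an uncommon sign of allergy, a few subjects can still matter, so the change is worth making, though it is not critical.

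**What to change.** Add one sentence to SAP 6.2.2 exempting rash from the maximal-severity rule for all ages and stating that a subject with any urticarial day in Days 1-7 counts as urticarial. In Tables 4.1.4-4.1.6 and 4.2.4-4.2.6, replace the 1/2/3 rash codes with two rows per subject: any urticarial rash on Days 1-7, and other rash only. The two rows then add up to any rash. Non-exclusive rows for the two types would also do, provided the SAP says so.

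First confirm two things: that the current Appendix 1 still carries the V4.0 key, and that the Diary Card and CRF record rash type by day. If type is recorded daily, the cost is one sentence and a changed row in six shells, with no new data. If type is recorded once per subject as a single choice, mixed weeks cannot be recovered in analysis, and the report should say so.

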For subjects < 6 years of age, the severity of systemic adverse events occurring up to 7 days after each vaccination will be categorized as follows. Change in eating habits : none (no change in appetite), mild (eating less than normal for 1 to feeds), moderate (missed 1 or 2 feeds), severe (missed more than 2 feeds); sleepiness : none (no change in alertness), mild (shows an increased alertness), moderate (sleeps through feeds), severe (sleeps most of the time and it is hard to arouse him/her); irritability : none (no change in child disposition), mild (requires more cudding and he/she is less playful than usual), moderate (more difficult to settle), severe (unable to console); rash : none, urticarial, or other; vomiting : none, mild (1-2 episodes/24 hours), moderate (>2 episodes/24 hours), severe (requires outpatient hydration); diarrhea : none (fewer than 2 loose stools/24 hours), mild (2-3 loose stools or < 400 gms/24 hours), moderate (4-5 stools or 400-800 gms/24 hours), severe (6 or more watery stools or > 800 gms/24 hours or requires outpatient IV hydration).

Body temperature will be categorized as <38°C (no fever), ≥38°C (fever) and will be summarized by 0.5°C increments from 36.0°C up to ≥40°C. Additionally, no fever vs. fever will be reported.

Each local and systemic adverse event will also be categorized as none vs. any.

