In case the Diary Card is not retrieved within 10 days after Day 29, subject or subject’s parent/legal representative will be contacted by phone to assess the occurrence of adverse events, determine the subject’s clinical status and complete study termination. All information will be recorded by the site staff on the subject’s medical record and collected in the appropriate section of the CRF.

All SAEs will be monitored until resolution and/or the cause is identified. If a SAE remains unresolved at study termination, a clinical assessment will be made by the investigator and the GSK regional physician to determine whether continued follow up of the SAE is needed.

Table 3.1-1: Safety Assessment Table

Medical History: All significant past diagnoses including all allergies, major surgeries requiring inpatient hospitalization, other significant injuries or hospitalizations, any conditions requiring prescription or chronic medication (i.e., >2 weeks in duration), or other significant medical conditions based on the investigator’s judgment.
	
From birth, collected at clinic visit Day 1

---	--

	CONFIDENTIAL :	Last Update Date
	THIS DOCUMENT AND INFORMATION CONTAINED HEREIN IS PROPRIETARY TO COMPANY AND IS NOT TO BE DISCLOSED WITHOUT THE WRITTEN PERMISSION OF COMPANY.	20-APR-2018
STATISTICAL ANALYSIS PLAN(V6.0)		

Immediate reactions: Subjects will be assessed for immediate hypersensitivity reactions.
	For at least 30 minutes after vaccination

Solicited local adverse events: < 6 years : injection site erythema, injection site induration, injection site tenderness ≥ 6 years : injection site erythema, injection site induration, injection site pain
	Days 1-7 after vaccination

Solicited systemic adverse events: < 6 years : change in eating habits, sleepiness, irritability, rash, vomiting, diarrhea, fever ≥ 6 years : chills, nausea, malaise, generalized myalgia, generalized arthralgia, headache, rash, fever
	Days 1-7 after vaccination
All unsolicited AEs will be collected	Days 1-7 after vaccination

Medically attended Adverse Events: Events that require a physician's visit or an emergency room visit (events that are managed by telephone or means other than a face-to-face evaluation by a clinician do not qualify as medically attended AEs).
	From Day 1 to study termination (Day 29/early termination)

Serious AEs: All SAEs will be collected.
	From Day 1 to study termination (Day 29/early termination)

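### SAP V6.0 defines mild sleepiness under 6 years as greater alertness, the reverse of the other grades, so the mild and any-sleepiness counts are misdefined as written

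*SAP*

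**What the plan says.** The Safety Assessment Table in SAP V6.0 section 2.4 lists sleepiness among the solicited systemic events for the younger group: "< 6 years : change in eating habits, sleepiness, irritability, rash, vomiting, diarrhea, fever". Section 6.2.2 then sets the grading. It opens with "For subjects < 6 years of age, the severity of systemic adverse events occurring up to 7 days after each vaccination", so the scale covers both the 2–23 month cohort and children aged 2 to 5 years. For sleepiness it reads "sleepiness : none (no change in alertness), mild (shows an increased alertness), moderate (sleeps through feeds", and the top grade is "severe (sleeps most of the time and it is hard to arouse him/her".

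The same section uses the grades in two ways. One is by worst grade: "Post-vaccination adverse events reported from Day 1 to Day 7 will be summarized by maximal severity". The other is a two-way split: "Each local and systemic adverse event will also be categorized as none vs. any".

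The latest table shells supplied, in SAP V4.0 Appendix 1, code the event by label only. The footnote to Table 4.1.4 reads "Mild(1), Moderate(2), Severe(3) : Change in eating habits, Sleepiness, irritability, vomiting, diarrhea", with no wording that would define mild differently.

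**The concern.** A severity scale has to run in one direction. Here the first step above none is "mild (shows an increased alertness", and the next two steps describe a child who sleeps too much. The sentence is the SAP's operative grading rule for this event, and section 5.1, where assessment criteria might otherwise stand, is marked not applicable.

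The slip sits at the grade that decides whether a child counts as having the reaction at all. It therefore reaches beyond one severity row to the any-sleepiness proportion. It also reaches the any-systemic-reaction rows for 2–23 months and 2–5 years (V4.0 shells, Tables 2.1.1 and 2.1.3), for children with no other systemic event. Someone reproducing the tables from the SAP alone would follow a rule that does not measure sleepiness.

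**Working it through.** The plan states no figure on this point, so the check is textual.

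**Step 1: apply the written grades to each possible state of a child.**

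| Worst state over Days 1–7 | Grade as written (6.2.2) | Grade the scale's direction implies |
|---|---|---|
| Usual alertness | None | None |
| More alert than usual, never drowsier | Mild | Not sleepiness |
| Drowsier than usual, not sleeping through feeds, never more alert | No grade fits | Mild |
| Sleeps through feeds | Moderate | Moderate |
| Asleep most of the time, hard to rouse | Severe | Severe |

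The third row fits nothing as written. It is not none, because alertness has changed. It is not mild, because alertness has not risen. It does not reach moderate or severe.

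**Step 2: carry this into the counts.** Let B be the number of children in the second row, C the third, D the fourth and E the fifth. A child who was more alert on one day and slightly drowsy on another is graded mild under either reading and cancels out.

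- Any sleepiness as written: B + D + E
- Any sleepiness as the scale implies: C + D + E
- Difference: (B + D + E) − (C + D + E) = B − C

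The mild row differs by the same B − C. If more children are slightly drowsy than unusually alert, the written rule undercounts. Even if B equals C, the children counted are the wrong ones. D and E are the same on both sides, so moderate and severe do not change. The documents give neither B nor C.

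**Step 3: look for text that corrects the wording.**

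- SAP V2.0, V3.0, V4.0 and V5.0 carry the same sentence in section 6.2.2, so this is not a damaged extract of one version.
- The V6.0 revision log records a wording revision across all sections, and the sentence came through unchanged.
- The shell footnotes give labels only.
- The supplied protocol body is the 11–55 year version; its solicited list has no sleepiness item.
- Protocol Amendment 1 says the under-6 events follow the sponsor's standards and are included in protocol version 2. The amendment text does not reproduce the grades, and version 2 is not supplied in full.

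Nothing supplied overrides the definition.

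**The case against.** The strongest reply is that this is a transcription slip with no effect on the data. The event is called sleepiness, and a parent would hardly report an unusually alert child under that name. The shells tabulate a recorded label, whereas for erythema and induration they print millimetre cut-offs. If the label chosen at collection is simply counted, the SAP sentence re-sorts nobody. The same paragraph has another plain slip: the mild grade for change in eating habits lacks a number. That points to careless copying and not to a chosen rule.

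Much of this stands, and it limits what can be claimed. A reader might infer that children have been misgraded or that the reported rates are biased. The documents do not show this, because the diary card, CRF and full amended protocols are not supplied and may carry the correct words. A reader might also want to attach a number by applying a rate to the 600 evaluable infants in section 2.2. No document gives a rate of mild sleepiness, and the 600 covers only 2–23 months, while the scale runs to age 5. For the same reason it would be too narrow to treat this as an infant-only problem. Nor is the whole scale unsound: three of the four grades are consistent.

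The reply does not rescue the text. If the forms are right, the SAP misdescribes the endpoint being reported. If the forms copied the sentence, the mild data have a problem that no one has flagged. Only a check of the forms can tell which.

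**Conclusion.** The definition is wrong as written, and the point is minor. For all subjects under 6 years, SAP V6.0 section 6.2.2 defines mild sleepiness in the opposite direction to the other grades. This misdefines the mild row and the none-versus-any count for that event; moderate and severe sleepiness are sound.

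The effect on results cannot be quantified. It is nil if the diary card and CRF used correct wording and the tables count the recorded grade. It is B − C children, both unknown, if the written definition was applied throughout. The conclusion rests only on the plain meaning of the sentence and on the absence of any correcting text in the supplied documents.

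**What to change.** First, compare the sleepiness grades in the diary card, the CRF and the amended protocol with section 6.2.2. This comes first because V6.0 took effect on 23 April 2018, about a month before the planned study end of roughly 22 May 2018, so rewording the SAP can do little to change how reactions were graded.

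Second, correct the SAP so that mild means reduced alertness (more drowsiness than usual) short of sleeping through feeds, in the same words as those forms.

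Third, if the faulty wording was used in data collection, footnote the mild and any-sleepiness results for subjects under 6 years to say so, and leave moderate and severe as they are.

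The cost is one phrase in the SAP and a check of existing forms, plus footnotes on the under-6 tables if the check turns up the error. Sample size, analysis sets and methods do not change.
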